**Prefrontal Cortical Engagement through Non-Invasive Brain Stimulation in Schizophrenia**

**Clinical Protocol: Version 5.0 BCM**

**Version Date: 4/12/2019**

---

Principal Investigator:	[name]
Study Coordinator:	[name]
Population:	Target sample Size is 100, male female, early schizophrenia diagnosis
Number of Sites:	Two sites. Baylor College of Medicine is the coordinating center site and the Michael E. DeBakey VA Medical Center is a secondary site.
Study Duration:	2 years
Subject Duration:	2 weeks

---

**SYNOPSIS**

Cognitive deficits are a strong predictor of functional outcome in schizophrenia, yet poorly remediated by current treatments. Disturbances in dorsolateral prefrontal cortex (DLPFC) function underlie core impairments such as in cognitive control and thus represent a critical target for novel therapeutics. Initial studies indicate transcranial direct-current stimulation (tDCS) may be effective in reducing symptoms due to DLPFC dysfunction. While tDCS potentially represents an exciting, novel therapeutic advance, a number of basic questions should be addressed prior to conducting larger-scale clinical trials, including: verifying therapeutic target engagement, optimizing treatment parameters, and evaluating for meaningful clinical effects.

**BACKGROUND**

[figure not shown]
This protocol is supported by a NIMH award that is organized into two phases. The goals of the first (R61) and second (R33) phases are to demonstrate target engagement and then clinical effect by the therapeutic intervention, respectively. Specifically, the primary goal of the R61 phase is to employ multimodal imaging to explicitly test for the assumed DLPFC engagement (fMRI) and modulation of frontal gamma activity (EEG) by tDCS, investigate the optimization of tDCS application parameters, and confirm the tolerability of tDCS for schizophrenia patients, and will be the focus of this protocol. After confirming that this effect is driven by tDCS effects in a positive direction, the current strength that has the highest effect size and also meets >80% completion rate will be the one that is selected for the R33 phase, which will seek to demonstrate clinical effect by assessing clinical outcomes scales and observing improvements in cognitive control mediated by DLPFC and frontal gamma oscillation engagement.

A successful outcome of this study would provide tDCS the sound mechanistic, methodologic and clinical-relevance basis for more definitive testing in large-scale clinical trials as a highly innovative therapeutic intervention for cognitive impairments in schizophrenia.

## OBJECTIVES AND HYPOTHESES

100 participants will undergo screening, and upon successful screening, be randomized to one of four treatment groups: 0mA (sham), 1.5mA, 2mA, and 2.5mA. Baseline measures of fMRI and EEG are taken before tDCS treatment. tDCS treatment is twice daily for five consecutive days. Following the last tDCS treatment, a posttest fMRI and EEG is conducted.

An overview of the study design is provided below:

### Primary Objective

- To investigate engagement of the DLPFC and frontal gamma oscillations as targets of frontal tDCS application in early schizophrenia patients. We will index the modulating effects of tDCS on DLPFC activity using fMRI BOLD imaging and gamma oscillations with EEG recordings in the context of cognitive control task performance.

### Secondary Objectives:

- To evaluate optimal strength (1.5 vs. 2.0 vs. 2.5 mA) in tDCS application for DLPFC engagement. Analogous to dose-finding in drug studies, we will conduct a parametric test for optimal current strength.
- To investigate the tolerability and feasibility of multi-session tDCS in schizophrenia. There is extensive evidence for tolerability of tDCS, confirmation for schizophrenia will be explicitly evaluated.

### Hypothesis

The primary hypothesis to be tested in this study is observing positive modulations in fMRI BOLD signals in the DLPFC and EEG frontal gamma oscillations during a cognitive control task following frontal tDCS modulation. We hypothesize tDCS application at 2.5 mA will show greatest engagement of DLPFC and frontal gamma oscillations and that 80% of subjects will complete the full tDCS protocol.

## OVERVIEW OF STUDY DESIGN

We aim to investigate transcranial Direct Current Stimulation (tDCS) as a novel therapeutic for cognition in psychosis. We will recruit 100 early phase schizophrenia patients with cognitive control deficits. A range of current strengths will also be explored, ranging from 1.5 to 2.5 mA in 0.5 mA increments. Thus, the subjects will be divided into four groups of N=25 for each of the tDCS current strengths including a sham stimulation (placebo) group.

We will recruit equal numbers of female and male participants. Subjects will have less than five years of treatment history and currently be on stable doses of second-generation antipsychotic medications for at least one month. Antipsychotic exposure history will be fully assessed and converted into standardized equivalents. The total duration of this study will be approximately 2 weeks. However, the majority of the study will be within a one week period.

Table 1: Overview of Study Design								
Procedure	Screening	Day 1	Day 2	Day 3	Day 4	Day 5	Day 6	Week 1
Medical, Medication History, Demographics, Color-blind screening	X							
Urine Screen	X							
MRI Screening Form	X							
Clinical Assessments	X							
Cognitive Assessments	X							
fMRI		X						X
EEG		X						X
tDCS			X	X	X	X	X	
Tolerability Assessment			X	X	X	X	X	
Comprehension Assessment	X	X	X	X	X	X	X	X
Payment	\$40	\$75	\$10	\$10	\$10	\$10	\$10	\$75
Total								\$240

**Screening:** Participants who provide written informed consent will undergo screening procedures and a review of the study eligibility criteria. At this visit the participant will complete the initial screening process, which includes detailed demographic information (including medication and treatment information), diagnostic information using the M.I.N.I diagnostic neuropsychiatric interview (M.I.N.I 7.0.2). Additionally, a cognitive assessment, MATRICS, will be conducted to assess level of cognitive functioning. Psychopathological ratings that are conducted include: the Brief Psychiatric Rating Scale (BPRS), the Scale for the Assessment of Positive Symptoms (SAPS), the Scale for the Assessment of Negative Symptoms (SANS) the 7-point Clinical Global Impression (CGI) Scale, the Global Assessment of Functioning (GAF). If participants meet the inclusion/exclusion criteria (see section Subject Population), participants continue to next visit.

**Day 1:** Experimenters will perform baseline fMRI and EEG procedures. Cognitive effects will be evaluated to assess acute effects of tDCS compared to baseline and to evaluate persistence. Subjects will undergo MRI in order to assist localization of EEG data and provide independent and complementary correlates of tDCS effects.

**Day 2- 6:** During these visits, the participants will undergo two 20 minute daily tDCS sessions, separated by 1 hour, for 5 consecutive days. Tolerability assessment will be administered to gauge how tolerable the tDCS session for the participant. Comprehension assessment will be administered to gauge the patients understanding of the study and to ensure they still have informed consent.

**Week 1:** Experimenters will perform posttest fMRI and EEG procedures. Cognitive effects will be evaluated to assess effects of tDCS compared to baseline and to evaluate persistence. Subjects will undergo MRI in order to assist localization of EEG data and provide independent and complementary correlates of tDCS effects.

**Payment:**

Participants who park in the Greenpark parking garage will have their parking tickets validated. Parking will also be validated at the MRI location.

Participant will be compensated for their time, as follows:

Visit 1: \$40 Visit 2: \$75 Visit 3: \$10 Visit 4:\$10 Visit 5: \$10 Visit 6: \$10 Visit 7: \$10 Visit 8: \$75 Total: \$240

A ClinCard will be used for study payments. Payments will be loaded onto the ClinCard within 48-72 hours of visit completion. The research study team will provide the participant with a handout about the ClinCard. The participants email address and/or cell phone number will be collected in the event they want email or text notification when payments are loaded to their ClinCard.

Baylor College of Medicine and Greenphire (ClinCard Company) have entered into an agreement which requires Greenphire to protect personal information.

The College will replace the participants ClinCard free of charge if their first card is lost or stolen. After that, there is a \$7 ClinCard replacement fee. This replacement fee will be charged to the balance on the participants ClinCard at the time of replacement. The participants ClinCard has an expiration date. If their ClinCard expires while they are participating in this study, Baylor will provide the participant with a new ClinCard at no cost. For a period of three months following the participants final study visit, they may request replacement of an expired ClinCard at no cost.

Payments for research participation are considered taxable income per Internal Revenue Service (IRS) regulations. If the total amount of payment received by the participant, the participant's parent, guardian or legally authorized representative (LAR) reaches or exceeds \$600 in a calendar year, Baylor College of Medicine will send an IRS Form 1099 to that person for tax purposes.

In order to issue the IRS Form 1099, Baylor will collect the participants first and last name, social security number, date of birth and home address. The name the participant provides should match the social security number. If the participant does not wish to provide a social security number, they can still participate in the study and decline all payment.

Study payments are considered income and may or may not affect government or public assistance benefit programs the participant or participant's parent, guardian or LAR may be participating in, such as SSI (Supplemental Security Income) or TANF (Temporary Assistance for Needy Families).

**SUBJECT POPULATION**

We will recruit 100 early phase schizophrenia patients with cognitive control deficits. We will recruit equal numbers of female and male participants across the Michael E. DeBakey VA Medical Center (MEDVAMC) and BCM. A range of current strengths will also be explored, ranging from 1.5 to 2.5 mA in 0.5 mA increments. Thus, the subjects will be divided into four groups of N=25 for each of the tDCS current strengths including a sham stimulation (placebo) group. We will recruit equal numbers of female and male participants. We have no hypotheses that relate to ethnicity or race. Minorities will be represented corresponding to or in slightly greater proportion to their prevalence in the Houston Metropolitan Statistical Area.

### Inclusion Criteria:

- a) ages 18-35 years;
- b) within first five years of antipsychotic treatment;
- c) on stable doses of antipsychotic medication for at least one month;
- d) Clinically stable as defined by Clinical Global Impression–Severity scale (CGI–S) less than or equal to 4 (moderately ill);e) MINI 7.0.2 criteria for schizophrenia or schizoaffective disorder

### Exclusion Criteria:

- a) Mental retardation as defined by pre-morbid IQ by Wechsler Test of Adult Reading at screening <70 or Spanish Word Accentuation Test;
- b) Significant head injury;
- c) History of severe medical or neurological illnesses;
- d) Pregnancy or postpartum (<6 weeks after delivery or miscarriage);
- e) Inability to provide informed consent;
- f) Significant color blindness that affects task performance;
- g) Currently on benzodiazepines or mood stabilizers affecting GABA
- h) Positive urine drug screen (excluding THC at baseline) or presence of substance abuse or dependence within 1 month;

Note: If a participant tests positive at Baseline for THC, they will not be automatically excluded. These individuals will be retested at the EEG/MRI appointment. During the EEG/MRI appointment, if they test positive for any substances they will not be allowed to complete the appointment and they will be withdrawn. The participants will be informed of this ahead of time.

### **Baylor College of Medicine Recruitment**

Subjects will be recruited from the outpatient clinical programs at Baylor College of Medicine and other community psychiatric programs. These will include Ben Taub's psychiatric emergency room and inpatient and outpatient center and MHMRA. Primary clinicians at BCM will be notified of our research study. Potential subjects with a diagnosis of schizophrenia will be identified and initially approached through their primary clinician, who will ask patient's permission to be contacted by the research team. Upon obtaining patient's written permission, a staff member from the research team will contact the subject. We will also recruit participants through flyers in the community, newspapers, social media (such as facebook), and BCM's clinical trials website.

Additionally, we will recruit from The Menninger Clinic who are aware of our clinical and research program. In addition to The Menninger Clinic, we will recruit from their affiliate "The Gathering Place". At The Gathering Place, members there will be shown presentations about research and will be provided research staff contact information. Consent to contact forms will be left at the facility so that members of The Gathering Place may later be contacted by research staff. Additionally, advertisements approved by their administration may be left at the facility.

## **Michael E. DeBakey VA Medical Center Recruitment**

All recruitment materials, consent forms, and Health Insurance Portability and Accountability Act of 1996 form will be approved by the MEDVAMC Research and Development Committee and the IRB prior to the beginning of the protocol. The study personnel will have certification of Human Subjects Research Training. Informed consent will be obtained prior to conducting any study procedures.

In-person recruitment will occur at Michael E. DeBakey VA Medical Center (MEDVAMC) and its related outreach clinics in the Houston area. Advertising materials will be posted in hospital bulletin boards and flyers/brochures will be distributed at VA events (e.g. VA Research Week Fair). To reach Veterans who do not visit the VA, recruitment flyers will be distributed on college campuses, community social media pages and newsletters, and at Veterans' Service Organizations (VSOs) events.

By pre-screening patients in CPRS, the research team can focus recruitment efforts on Veterans who are more likely to qualify for the study. Pre-screening involves interviewing the patient to check for inclusion/exclusion criteria. (Veterans who are referred or recruited through flyers may be pre-screened through CPRS chart review or over the phone).

Individuals who satisfy the pre-screen requirements will be mailed an invitation letter with information about the study. The letter will include an option to opt-out from being contacted about the study. Approximately two to three weeks after mail-outs, a study coordinator will follow-up with candidates who were sent invitation letters. Veterans who opted out will not be called. Additionally, psychiatrist will be contacted, for patients who have upcoming appointments, in order to obtain consent to contact from the patient.

Alternatively, participants will be recruited by information booths set up in the outpatient psychiatry clinic. Inpatient units of MEDVAMC will be an additional recruitment source; in the case that an individual within MEDVAMC's inpatient facility might be eligible for the study, staff will reach out to the patient's doctor to determine if the doctor feels the patient would be a good fit for the study and when the patient's discharge is predicted to be. With doctor approval, staff will speak with the patient at discharge to determine their interest and follow up at a later date.

Interested individuals will be scheduled to meet with the PI and/or a research team member to discuss the study's goals and procedures in detail. After meeting the PI/research team member, Veterans who wish to enroll will be scheduled to start the study. Meeting the PI/coordinator before enrolling in the study allows the individual extra time to consider his/her decision to participate and reduces the risk of coercion or undue influence.

When the participant is ready to enroll in the study, he/she will review the consent document and be given ample time to ask questions. Participants will also be reminded that participation is voluntary and will not affect their access to healthcare or benefits. A copy of the signed consent form will be given the participant. No study procedures (structured screening or testing) will commence prior to obtaining informed consent.

### **Recruitment Milestones**

We plan to frontload recruitment with a target of 60 participants in the first year and the remaining 40 in year two. This strategy will leave time in year two to finalize analyses, address the transition criteria to the R33 phase, and prepare abstracts and manuscripts related to the R61 aims.

## **TREATMENT ALLOCATION AND BLINDING**

### **Randomization, Blinding and Tolerability Assessments**

Subjects will be randomly assigned to one of the three active tDCS (1.5 mA, 2.0 mA or 2.5 mA) or sham groups (N=25/group), under the constraint of group-level demographic and cognitive status matching. For robust blinding, we will coordinate three different teams of experimenters, responsible for 1) clinical/neuropsychological status evaluations; 2) tDCS application; and 3) EEG/fMRI recording and data analysis. Critical to our third aim, the second team will be responsible for assessing tolerability during the stimulation and general adherence to the stimulation sessions. We will employ a “triple-blind design” in the following manner to minimize unintended biases/confounds: randomized group assignment; automatic, computer control of the stimulator according to the encrypted subject’s group; de-identified data analysis.

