### **STATISTICAL METHODS**

**Primary Objective:** Dependent measures will be task condition-related differences in fMRI BOLD activation as measured through GLM and EEG oscillatory activity in the gamma band as analytically estimated by complex wavelet transformation. Group and time point differences will first be assessed with omnibus tests instantiated through the general linear model (e.g., repeated measures ANOVA) to determine the presence and direction of potential effects. Effects equivalent to  $f \geq .16$  will be targeted. To determine the efficacy of the treatment conditions, we plan to conduct post-hoc comparisons of the post- minus pre-test differences between each active stimulation group and the sham stimulation group, as well as within each group between the post- and pre-test measures. The behavioral context of these changes will also be assessed by the Inc-Con difference in accuracy and reaction time in an analogous manner to fMRI and EEG measures.

**Secondary Objective:** Initial analytical targets will be identified concurrent with Aim 1. Polynomial trend analyses will be used to determine the dose-response curve to tDCS. To assess the degree of efficacy of each treatment, Cohen's  $d_z$ , a measure of effect size similar to Cohen's  $d$  which also accounts for the covariance between measures, will be calculated within each group based on the difference between control-related activations from the pre- and post-test assessments with an ideal target of  $d_z = .534$  for fMRI BOLD activation and  $d_z = .687$  for EEG gamma synchrony (i.e., half the observed distance between patient and control measures based on preliminary data). As an exploratory analysis, we will also make use of the structural MRIs to create individualized head models of current strength in the DLPFC. Since the current strength, distribution and even polarity can vary considerably as a function of individual physiology and anatomy, such comparisons between the predictive value of the tDCS device's current output vs. the modeled current strength in relation to the fMRI

and EEG measures will be invaluable in informing future investigations of personalized treatment protocols and tDCS tolerability/safety.

**Tertiary Objective:** A target completion rate of 80% serves as our benchmark for assessing feasibility. No analysis is required - this benchmark will simply serve as the required threshold for starting the R33 phase.

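### Allocation is matched on demographic and cognitive status but the between-group analysis names only group and time point; if the matching variables predict change, those tests are conservative and lose some power

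*Combined protocol and SAP*

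**What the plan says.** The cover page gives the size ("Target sample Size is 100"), and the Overview of Study Design states that "the subjects will be divided into four groups of N=25". The section on Randomization, Blinding and Tolerability Assessments says that assignment to the three active arms or sham is random, but "under the constraint of group-level demographic and cognitive status matching". It names neither the variables nor the algorithm.

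Under Statistical Methods, Primary Objective: "Group and time point differences will first be assessed with omnibus tests instantiated through the general linear model (e.g., repeated measures ANOVA". This is followed by "post-hoc comparisons of the post- minus pre-test differences between each active stimulation group and the sham stimulation group", and by comparisons "within each group between the post- and pre-test measures". No section names a covariate or says that the matching variables enter the model. No section rules them out either, and the repeated measures ANOVA is offered only as an example.

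**The concern.** Constrained allocation makes the arms more alike on the matching variables than simple randomisation would. Whatever those variables contribute to the outcome is then largely removed from the differences between arms. A model without them leaves that contribution in the residual, so its standard error describes an allocation scheme that was not used.

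The error is in the safe direction: the true type I error falls below its nominal level and the intervals are too wide. The price is power, in a trial with 25 per arm. There is also a choice left open. If the plan does not say whether the matching variables are in the model, that decision can be made after the data are seen.

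**Working it through.** **The plan's own figure.** The total of 100 with a target of f ≥ .16 cannot be reproduced from the documents, because alpha, power and the pre-post correlation ρ are not stated. For the group-by-time test with 4 groups and m = 2 visits, λ = f²·N·m/(1−ρ) on 3 and 96 df. With alpha .05 and power .80 assumed, N = 100 follows only if ρ is about .55: λ = .0256 × 100 × 2/.45 = 11.4, power .801. At ρ = .50, λ = 10.24, power is .753 and 112 would be needed. The plan therefore gives no stated power against which to measure a loss.

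**What matters is prediction of change.** With two visits, the group-by-time test is a one-way ANOVA of post minus pre. A variable that shifts both visits equally cancels. Let R2 be the share of change-score variance explained by the matching variables. The documents do not give it, so a range of 0 to .20 is assumed.

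**Closed form, perfect balance.** In units of the SD of change, the unadjusted standard error of an active-versus-sham contrast is √(2/25) = .283. The true standard error is .283·√(1−R2), and the type I error of the unadjusted two-group test is 2·[1 − Φ(1.96/√(1−R2))].

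| R2 | True SE | 1.96/√(1−R2) | Type I, unadjusted |
|---|---|---|---|
| 0 | .283 | 1.960 | .050 |
| .05 | .276 | 2.011 | .044 |
| .10 | .268 | 2.066 | .039 |
| .20 | .253 | 2.191 | .028 |

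**Simulation, imperfect balance.** Assumed: 100 participants, four arms, minimisation on sex, age and cognition, 3-df omnibus test on change at .05. For power, the effect is .687 SD of change in all three active arms and none in sham. The value .687 is borrowed from the plan's EEG d_z target. Power run A used 6,000 trials per cell; run B is a separate simulation, which also gave the type I errors.

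| R2 | Type I, unadjusted / adjusted | Power A (%), unadjusted to adjusted | Power B (%), unadjusted to adjusted |
|---|---|---|---|
| 0 | .047 / .048 | 68.4 to 68.1 | 69 to 68 |
| .05 | .044 / .050 | 68.4 to 70.1 | 70 to 72 |
| .10 | .037 / .048 | 67.6 to 71.8 | 68 to 73 |
| .20 | .030 / .053 | 67.6 to 78.0 | 68 to 79 |

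The gain from adjusting is about nil at R2 = 0, 2 points at .05, 4 to 5 at .10 and 10 to 11 at .20.

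A noncentral F check agrees. λ = 25 × .75 × .687² = 8.85, which gives power .683 on 3 and 96 df. With three covariates and perfect balance, λ/(1−R2) on 3 and 93 df gives .683, .708, .733 and .788 at R2 = 0, .05, .10 and .20.

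**A different algorithm.** Taking the best balanced of 100 random allocations on three covariates, the unadjusted standard error of one active-versus-sham contrast was overstated by about 0, 1, 3 and 8% at the same R2 values. At R2 = .20 its type I error was .036, and power for an assumed 0.8 SD effect rose from .82 to .87 with adjustment.

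**Form of the covariate term.** In a repeated measures model a covariate main effect adds the same amount to both visits, so it drops out of the group-by-time test. In one simulated dataset, the 2.5 mA-by-time estimate (SE) was 0.524 (0.368) without the covariate, identical with its main effect, and 0.597 (0.343) with a covariate-by-time term.

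**The case against.** The strongest objection is that no loss has been shown. The outcome is already a difference between task conditions, and the between-group contrasts are then made on the difference between visits. Demographic or cognitive effects common to both conditions or both visits cancel, so R2 for change may be close to zero. At .05 to .10 the standard error is overstated by only 1 to 3% in the best-of-100 check. Nothing in the documents supports a value near .20, where the gain becomes large. This stands, and it is why the point is conditional.

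A reader might infer that the error bars are too wide as a matter of fact, or that the balance achieved by matching is thrown away. The documents support neither. The first depends on an association with change that they do not report. On the second, the point estimate keeps its balance; what may go unrecognised is the gain in the reported standard error and p-value.

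A reader might also infer that the phase-transition decision is compromised. It is not. The R61 to R33 Phase Transition Criteria require f ≥ .16, a positive direction and more than 80% completion, and name no p-value or interval. The d_z for each current is computed within an arm, where matching between arms plays no part.

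Finally, the analysis text is silent on covariates and does not exclude them. That is true, so this is an omission and not a stated error. Silence still leaves the choice between adjusted and unadjusted models open until the data are in hand.

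**Conclusion.** The mismatch is real: the trial allocates by variables that its analysis text does not mention. Its consequence is conditional. If the matching variables predict post-minus-pre change, the omnibus group-by-time and active-versus-sham tests are conservative and give up some power; if not, nothing is lost. Over R2 of 0 to .20, unadjusted type I error runs from about .05 down to .03, and adjustment gains about 0 to 11 power points.

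These figures rest on an assumed R2 range, an assumed minimisation on sex, age and cognition, alpha .05 and an effect of .687 SD in every active arm. The protocol specifies neither the algorithm nor the variables, and cognitive status could mean the MATRICS score or the IQ measure. There is no bias and no inflation of type I error. The point is worth considering because the remedy is nearly free; it is not a flaw that undermines the trial.

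**What to change.** - In Statistical Methods, Primary Objective, state that the between-group analysis of post-minus-pre change includes as covariates the variables used to constrain allocation. If the repeated measures form is kept, specify them as covariate-by-time terms.
- In Randomization, Blinding and Tolerability Assessments, name those variables and the allocation method.
- State that the f used for the Go rule is computed on the unadjusted SD, so that the meaning of .16 does not shift.

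The cost is a few sentences and about 3 to 4 error degrees of freedom out of 96. Demographics, MATRICS and IQ are already collected at screening. If the variables turn out not to predict change, the simulated loss of power from adjusting is at most about 1 point.
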